**CONFIDENTIAL**

056-F275 Rev G Clinical Investigation Plan Template

# Enable Hernia Repair Clinical Investigation Plan

MDT21022

Version 5.0

Page 34 of 116

Medtronic

[name].

## Medtronic Hugo™ RAS system-Compatible Components:

The following components are required, if applicable, for study procedures and will be provided by the study sponsor (Table 5).

**Table 5. Medtronic Hugo™ RAS system-Compatible Components**

SKU	Product Description (Manufacturer)	Investigational or Commercially Available
TC200EN	Storz 3D Camera Control / System (Karl Storz)	Commercially Available
TC302EN	Storz 3D SCB Interface & Spies System (Karl Storz)	Commercially Available
TL 300	Storz Cold Light Fountain Power LED 300 (Karl Storz)	Commercially Available
26605BA	Storz 30 Degree 3D Endoscope (Karl Storz)	Commercially Available
26605AA	Storz 0 Degree 3D Endoscope (Karl Storz)	Commercially Available
495VIT	Storz Fiber Optic Light 5.5m Cable (Karl Storz)	Commercially Available
TC015	Storz Video Extension Cable (Karl Storz)	Commercially Available
VLFT10GEN	FT-10 Generator (Covidien)	Commercially Available
FT0510	Reusable Monopolar Electrosurgery Cord (Covidien)	Commercially Available
E0020V	Reusable Bipolar Electrosurgery Cord (Covidien)	Commercially Available
RUNVCA8STF	VersaOne™ Universal Cannula Positioning Trocar System – 8mm standard Universal Fixation Cannula (Covidien)	Commercially Available
RNONB8STF	VersaOne™ Bladeless Positioning Trocar System – 8mm standard fixation trocar (Covidien)	Commercially Available
RONB11STF	VersaOne™ Optical Positioning Trocar System – 11mm standard fixation trocar (Covidien)	Commercially Available
RSEAL	VersaOne™ Reusable Positioning Trocar System – 5mm - 12mm Seal (Covidien)	Commercially Available
OBTNONB8ST	VersaOne™ Reusable Positioning Trocar System – 8mm standard Bladeless Obturator (Covidien)	Commercially Available

*Medtronic Business Restricted*

**CONFIDENTIAL**

056-F275 Rev G Clinical Investigation Plan Template

# Enable Hernia Repair Clinical Investigation Plan

MDT21022

Version 5.0

Page 35 of 116

Medtronic

OBTONB11ST	VersaOne™ Reusable Positioning Trocar System – 11mm standard Optical Obturator (Covidien)	Commercially Available
RC8STS	VersaOne™ Reusable Positioning Trocar System – 8mm standard Reusable Positioning Cannula (Covidien)	Commercially Available
RC11STS	VersaOne™ Reusable Positioning Trocar System – 11 mm standard Reusable Positioning Cannula (Covidien)	Commercially Available
KSZ-39301TS	Endoscope Sterilization Tray	Commercially Available

## Mesh:

- The choice of the mesh is at the surgeons' discretion depending on their local standard of care for this indication. The mesh will not be provided by the study sponsor and should be used in accordance with the instructions for use.

## Other Equipment:

The following components may be required for the study procedures and will not be provided by the study sponsor.

- Energy Sealing Device
- Linear Stapler
- Reticulating Stapler
- Surgical Clips

## 7.6 Product Use

This information is contained in the Hugo RAS system User Guide and accompanying labeling (**Appendix 18.3**). The User Guide and additional labeling should always be consulted.

The device will be in contact with the abdominal region including tissues and body fluids. All device components and materials are biocompatible. Device biocompatibility testing and results are summarized in the RPI (**Appendix 18.2**).

For instructions on study product scope of use and handling, please refer to the IFU (**Appendix 18.3**).

## 7.7 Product Training Materials

The Medtronic Hugo™ RAS system should only be used by surgeons and OR staff who have received specific product training provided by Medtronic in the use of this device (**Table 6**). The training provided by Medtronic does not replace the necessary medical training and experience required to perform

*Medtronic Business Restricted*

**CONFIDENTIAL**

056-F275 Rev G Clinical Investigation Plan Template

surgery.

Surgeons and hospital staff performing study procedures will be required to demonstrate a minimum level of professional competency and product training outlined below prior to performing study procedures.

**Technical Training** focus areas include:

- Hugo™ System Operation
- Hugo™ System Surgical Field Set-up
- Hugo™ System Console Skills
- Hugo™ System Clinical Application
- RAS Fundamental Surgical Task Skills

**Table 6. Professional Competency and Product Training**

	Professional Competency	Product Training
Principal Investigator(s)	
 
• At least 2 years of surgical training and/or experience conducting laparoscopic surgery
 
• At least 2 years robotic experience with the specific study procedure(s) they will be performing for the study
 
• On average, completing 10-12 procedures annually (specifically the study procedure (s) they will be performing for the study)
 
	
 
• Completed simulator exercises on the Medtronic Hugo™ RAS system
 
• Didactic training on the capability and features of the Medtronic Hugo™ RAS system
 
• Completed hands-on training course
 

OR Staff	
 
• At least 2 years of surgical training and/or experience in robotic surgery
 
	
 
• Didactic training on the capability and features of the Medtronic Hugo™ RAS system
 
• Completed hands-on training course
 

All study site personnel will be trained on relevant information prior to their participation in the study.

Surgeon proctoring will be provided to the Investigators as directed by Medtronic Robotic Surgical Technologies. Medtronic personnel may be present for the investigational implants at the sites.

## 7.8 Product Receipt and Tracking

The Medtronic Hugo™ RAS system and necessary equipment will be shipped to each site and tracked. In the case that model, lot, and/or serial numbers are not available on the packaging, the sponsor will assign lot, batch, or serial numbers to the study product to maintain traceability. Each site will review the content

*Medtronic Business Restricted*

of the shipping form and investigational product upon receipt. The use of the device for a procedure or disposition of the devices (e.g., if returned due to damage upon arrival) will be recorded on a site device accountability log to be maintained at the site and reconciled by the end of the study.

The Medtronic Hugo™ RAS system and necessary instruments will be provided to each site upon sponsor collection and approval of all required regulatory documents.

The date when the site receives the Hugo™ RAS system, will be recorded and maintained during the clinical investigation. Each Medtronic Device and Device Instrument will be traced with the serial or lot number.

## 7.9 Product Storage

Access to the study should be limited to designated study staff only. Study device components should be covered with sponsor provided device covers when not in use for study procedures.

Study devices should be kept in or otherwise contained where only qualified study personnel can access the device (i.e., locked or secured). This area/container should be kept at ambient temperatures without exposure to water with adequate provisions for maintaining ambient temperatures if a loss of power is experienced. If the devices are exposed to water or a drastic change in temperature, sites should contact the study team for possible replacement devices.

## 7.10 Product Return

It is the responsibility of the site to return the Medtronic Hugo™ RAS system to Medtronic at the end of the study, along with any unused or expired Medtronic Hugo™ RAS wristed instruments or other components. Sites should follow instructions and complete all appropriate forms provided by the study team for product return.

## 7.11 Product Accountability

Access should be limited to designated study staff only. A device accountability log will be maintained at the site and reconciled by the end of the study. It is the site's responsibility to document the receipt (which includes shipping/dispersal date, the quantity, model, lot, and serial numbers, and expiration date), disposition of the product (per subject use, including amount used, amount remaining, etc.), transfer (if applicable), and return of all unopened investigational medical devices at the end of the study. The sponsor shall also keep records to document the physical location of all investigational devices from shipment of investigational devices to the investigation sites until return or disposal. Medtronic will perform periodic reconciliation of the investigational product to ensure traceability through monitoring.

## 8 Study Site Requirements

### 8.1 Investigator/Investigation Site Selection

All Investigators managing the subject's hernia repair must be qualified practitioners and experienced in the diagnosis and treatment of subjects with inguinal or ventral hernias. All physicians must be experienced and/or trained in the handling of the Medtronic Hugo™ RAS system.

The role of the Principal Investigator is to implement and manage the day-to-day conduct of the clinical investigation as well as ensure data integrity and the rights, safety and well-being of the subjects involved in the clinical investigation.

The Principal Investigator shall:

- Be qualified by education, training, and experience to assume responsibility for the proper conduct of the clinical investigation
- Be experienced in the field of application and training in the use of the Medtronic Hugo™ RAS system
- Disclose potential conflicts of interest, including financial, that interfere with the conduct of the clinical investigation or interpretation of results
- Be able to demonstrate that the proposed investigational study site:
  - Has the required number of eligible subjects needed within the recruitment period
  - Has one or more qualified Investigators, a qualified investigational study site team and adequate facilities for the foreseen duration of the clinical investigation

Study site personnel training will be completed and documented prior to participation in this study.

### 8.2 Study Site Activation

During the activation process (prior to subject enrollment), Medtronic will train study site personnel on the clinical investigation plan (CIP), on relevant standards and regulations, informed consent, and on data collection and reporting tools. If new members join the study site team, they will receive training on the applicable study requirements relevant to their role before contributing to the study.

Prior to performing study related activities, all regulatory requirements shall be fulfilled, including, but not limited to the following:

- Institutional Review Board (IRB) approval (and voting list, as required by local law) of the current version of the CIP and informed consent (IC).
- Regulatory Authority (RA) approval or notification (as required per local law)
- Fully executed Clinical Trial Agreement (CTA)
- Financial disclosure (if applicable)
- Curriculum vitae (CV) of Investigators and key members of the investigation study site team (as required). The signature on the CV must be dated within 3 years prior to the date of activation of the study site.
- Documentation of delegated tasks

*Medtronic Business Restricted*

- Documentation of study training
- Additional requirements imposed by local regulations, the IRB and RA shall be followed, if appropriate

In addition, all participating study site staff must be trained on the current version of the CIP as well as on the applicable study requirements depending on their role and must be delegated by the Principal Investigator to perform study related activities.

Medtronic will provide each study site with documentation of study site/investigator readiness; this letter must be received prior to performing study related activities.

### 8.3 Role of the Sponsor Representatives

In addition to performing monitoring and auditing activities, sponsor representatives may provide support at the study site as required for the study under supervision of the Principal Investigator, including:

- Provide study training relevant and pertinent to the involvement of personnel conducting study activities and Investigator responsibilities.
- Technical support will be provided during the procedure under the supervision of a study Investigator, but no data entry, shall be performed by Medtronic personnel or their representatives at study sites.

In addition, for this study, sponsor representatives may be authorized by the Principal Investigator to perform the following significant trial related duties:

- Support study Investigators in performing the study implant procedure.
- Support data collection during the implant procedure and device testing.
- Support data collection during the study follow-up visits.

Any data collection completed by Medtronic personnel will be clearly identified as such.

## 9 Selection of Subjects

### 9.1 Study Population

Up to 192 subjects will be enrolled at up to ten sites in the US.

The Medtronic Hugo™ RAS system is intended to be used in this study for robotic assisted hernia repair procedures, including procedures to be performed in subjects that meet the inclusion criteria listed in **Section 9.3**.

Subject conditions and/or diagnoses may include, but are not limited to, inguinal and ventral hernia repair.

The subjects must be acceptable candidates for a fully robotic assisted procedure with the Medtronic Hugo™ RAS system, as determined by the investigating surgeon.

*Medtronic Business Restricted*

**CONFIDENTIAL**

056-F275 Rev G Clinical Investigation Plan Template

## 9.2 Subject Enrollment

A subject is considered enrolled in the study when the informed consent form is signed and dated. As soon as the surgical procedure has begun with the Medtronic Hugo™ RAS system, the subject must be followed regardless of whether the subject completed the surgical procedure with the Medtronic Hugo™ RAS system. Subject enrollment will be consecutive at the institution according to required procedure types and eligibility criteria. See **Section 14** for additional details.

## 9.3 Inclusion Criteria

1. Adult subjects (age  $\geq 22$  years) as required by local law
2. Subject has been indicated for one of the following hernia repairs:
  - a. primary or incisional ventral hernia(s). Multiple small hernia defects are allowed with total distance of combined defects being  $< 10\text{cm}$  (**Figure 2: A and B**)
  - b. inguinal (unilateral or bilateral) hernia(s)
3. Subject is an acceptable candidate for a fully robotic assisted surgical procedure, a laparoscopic surgical procedure, or an open surgical procedure
4. The subject is willing to participate and consents to participate, as documented by a signed and dated informed consent form

## 9.4 Exclusion Criteria

1. Subjects for which minimally invasive surgery is contraindicated as determined by the Investigator
2. Subjects with a recurrent hernia
3. Subjects with femoral hernia defects
4. Subjects with ventral hernia defect(s) located in M1, M5, or L4 (**Figure 2: C and D**)
5. Subjects with emergent hernia repair
6. Ventral hernia is CDC grade 2 or higher
7. Use of component separation techniques to close the hernia defect
8. Inability to close the defect in ventral hernia subjects
9. Hernia defect is  $\geq 10\text{ cm}$
10. Subject has BMI  $> 40$
11. Subjects with comorbidities or medical characteristics, which would preclude the surgical procedure in the opinion of the Investigator
12. Subjects diagnosed with a bleeding disorder and/or cannot be removed from their anticoagulants prior to surgery based on surgeon discretion and standard-of-care
13. Subjects pregnant at the time of the surgical procedure
14. Subjects who are considered to be part of a vulnerable population (e.g., prisoners or those without sufficient mental capacity)
15. Subjects who have participated in an investigational drug or device research study within 30 days

*Medtronic Business Restricted*

of enrollment that would interfere with this study

16. Subjects with active infections including but not limited to pneumonia, urinary tract, cellulitis, or bacteremia

## Classification of Abdominal Wall Hernias

[figure not shown]

Figure 2: A and B – Definition of the width and length for single hernia defects and multiple hernia defects, respectively. C – To classify midline hernias, five zones were defined. D – To classify lateral hernias, four zones were defined 

## 10 Study Procedures

### 10.1 Schedule of Events

#### 10.1.1 Screening Visit (Visit 1)

A screening visit will be performed within 30 days prior to the scheduled procedure and may be combined with the surgical procedure visit. Subjects will be consented before any procedures specific to the study are undertaken. The purpose and all aspects of the study will be explained to the subject. Subjects who agree to study participation must sign and personally date an IRB-approved informed consent form prior to participating in any study activities.

Once informed consent has been obtained according to IRB requirements and eligibility is confirmed, the subject's demographics and medical history will be assessed. Relevant medical and surgical history will be assessed and included in the electronic case report form (eCRF). All efforts to screen a diverse subject population should be made.

#### 10.1.2 Surgical Procedure Visit (Visit 2)

The subject will arrive for admission to the hospital, will be checked in, placed in pre-op, and prepped for surgery according to local standard of care. Upon arrival to the operating room the subject will be placed on the plinth, the anesthesia and surgical teams will place the subject in position and the operation will begin at the time of the first incision. The study Investigator should perform the surgical procedure according to the appropriate standard procedures, practices, and set-up guidelines. See **Table 7** for the data that will be collected during this procedure.

#### 10.1.3 Up to Hospital Discharge (Visit 2.1)

Visit 2.1 will begin when the subject arrives in recovery after the operation is over and will last through the subject being discharged from the hospital. All standard-of-care practices will be followed for this visit. See **Table 7** for the data that will be collected during this procedure.

#### 10.1.4 Post-Operative Follow-Up Visit (Visit 3)

The 30 ( $\pm 7$ ) days post-operative visit should be made by an in-person follow-up visit to the site.

Only in extreme circumstances (e.g., COVID-related in person restrictions at the site, etc.), the 30 ( $\pm 7$ ) day follow-up visit may be conducted via phone call and/or video conference for the collection of adverse event and medical follow-up information.

#### 10.1.5 Post-Operative Follow-Up Visit (Visit 4)

The 3-Month ( $\pm 14$  days) post-operative visit should be made by an in-person follow-up visit to the site.

Only in extreme circumstances (e.g., COVID-related in person restrictions at the site, etc.), the 3-Month

*Medtronic Business Restricted*

(±14 days) day follow-up visit may be conducted via phone call and/or video conference for the collection of adverse event and medical follow-up information.

## 10.1.6 Post-Operative Follow-Up Visit (Visit 5 and 6)

Post-operative visits 5 at 1 year (±30 days) and 6 at 2 years (±30 days) will be made via phone call. It is permissible for the visits to be conducted in person if it coincides with a standard of care office visit.

Subjects who report a hernia recurrence or an AE that requires investigator assessment must then complete an in-person office visit. If this occurs, the rest of the visit data in this section may be collected either over the phone or in person. If collected in person, the visit should still be entered in the eCRF as a standard follow-up visit. Importantly, data listed below should be collected only once per annual visit whether collected via phone, in person, or combination of both. If any data is collected out of window, a protocol deviation should be reported.

Every attempt must be to have all subjects complete the follow-up visit schedule. For subjects who do not show up for a scheduled study visit, the site must contact the subject in a timely manner to reschedule the visit and associated required evaluations within the subject's window, if possible.

In cases where the required attempts to make contact have been unsuccessful but there is no evidence that the subject has expired, sites will complete a Protocol Deviation for Visit Not Done and attempts to contact subjects will be made again the following year. Also refer to **Section 10.10.3 - Lost to Follow-up**.

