***Medtronic Business Restricted***

palpable fascial defect and/or a clinically manifested bulge within 7 cm of the original repair, exacerbated by a Valsalva maneuver during physical examination by a study investigator.

The following long-term secondary endpoints will be assessed through 2 years post-procedure in all treated subjects:

- Recurrence rate through 2 years post-procedure
  - Note: Suspected hernia recurrence(s) reported by a subject, but not confirmed by an investigator, will not be considered as a clinical hernia recurrence for this endpoint, but will be reported separately as a subject-reported recurrence.

Clinical hernia recurrence is defined as a palpable fascial defect and/or a clinically manifested bulge within 7 cm of the original hernia repair, exacerbated by a Valsalva maneuver during physical examination by a study investigator.

- Hernia recurrence will be evaluated by physical examination and confirmed, if deemed necessary, by a study investigator following site standard of care for medical imaging of hernia evaluation.
- If standard of care imaging (Computerized Tomography Scan (CT scan), ultrasound, or Magnetic Resonance Imaging (MRI)) is done for hernia recurrence confirmation, at the discretion of the study investigator, the final decision to report a clinical hernia recurrence will be based on the study investigator's assessment. Standard of care imaging may be done by a non-study, standard of care assessor, such as a radiologist.
- Secondary hernias will need to be differentiated from primary hernia recurrences by a study investigator. Secondary hernias are defined as a hernia located >7 cm of the original hernia repair. Secondary hernias will be excluded from hernia recurrence reporting for all hernia recurrence endpoints, but will be captured on an adverse event electronic case report form (eCRF).

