## Performance Goals for Long-term Secondary Endpoints (through 2 years)

**Table 16: Recurrence Rate through 2 Years – Performance Goal Determination**

Long-term Secondary Endpoint: Hernia Recurrence Rate			
Endpoint	Surgery Type (Inguinal, Ventral Hernia)	PG	Rationale
Recurrence rate (through 2 years)	Inguinal Hernia Repair	15%	This analysis was based on eight cohorts. The effect size index is the mean recurrence rate. The mean effect size is 0.6% with a 95% CI of 0.2 to 1.3%. If we assume that the true effects are normally distributed (in logit units), we estimate that the 95% prediction interval is 0.2 to 1.7%. The PG for recurrence through 30 days is set at 8%. Adding a 7% clinical margin to the 30-day PG, we set the 2-year PG at 15% for reoperation rate through 2 years following inguinal hernia repair.
	Ventral Hernia Repair	37%	This analysis was based on seven cohorts. The effect size index is the mean recurrence rate. The mean effect size is 10.9% with a 95% CI of 4.7 to 23.1%. If we assume that the true effects are normally distributed (in logit units), we estimate that the 95% prediction interval is 1.3 to 53.6%. We set a PG of 37% recurrence rate through 2 years following ventral hernia repair, which falls between the upper bounds for the 95% CI and 95% prediction interval and is clinically relevant.

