Recurrence rate through 2 years post procedure	This analysis uses similar definitions as recurrence rate through 30 days. Note: Suspected hernia recurrence(s) reported by a subject, but not confirmed by an investigator, will not be considered as a clinical hernia recurrence for this endpoint, but will be reported separately as a subject-reported recurrence in the final report.

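### Two-year recurrence needs an investigator's examination, but after 3 months that examination mainly follows the subject's own report; refuted and never-examined reports are treated alike, and the denominator is not stated

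*Protocol*

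**What the plan says.** **Definition.** CIP 5.2.2 defines clinical recurrence as a palpable defect or a bulge within 7 cm of the repair, "exacerbated by a Valsalva maneuver during physical examination by a study investigator". SAP 4.2.1 and 7.9.3.1 repeat this, and SAP 7.9.3.1 admits only confirmed recurrences to the rate.

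**Schedule.** The 30-day and 3-month visits are in person except in extreme circumstances (CIP 10.1.4, 10.1.5). For the later contacts, CIP 10.1.6 says that visit 5 at 1 year and visit "6 at 2 years (±30 days) will be made via phone call". Two routes to an examination remain:
- by coincidence: "It is permissible for the visits to be conducted in person if it coincides with a standard of care office visit";
- by self-report: "Subjects who report a hernia recurrence or an AE that requires investigator assessment must then complete an in-person office visit".

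Table 7 of the CIP still lists recurrence as collected in the column for the phone visits.

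**Unconfirmed reports.** CIP 5.2.2: "Suspected hernia recurrence(s) reported by a subject, but not confirmed by an investigator, will not be considered as a clinical hernia recurrence for this endpoint". SAP 7.9.3.1 has the same rule and adds that such a report "will be reported separately as a subject-reported recurrence in the final report".

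**Denominator.** CIP 14.5 speaks of all treated subjects and also of FAS subjects with available data, and SAP 7.9.3.5 of the latter. SAP 7.4 says in detail what counts as available at 30 days. There is no matching rule for 2 years.

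**Benchmark.** Table 16 of the CIP sets 15% for inguinal repair; for ventral repair it says "We set a PG of 37% recurrence rate through 2 years following ventral hernia repair". CIP 14.5 and SAP 7.9.3.3 describe these figures as aids to interpretation, not success thresholds.

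**The concern.** The endpoint is defined by a clinical finding, but from year 1 on that finding is looked for mainly in subjects who say they have a problem. Cases can be missed in two ways. A subject may have a defect that an examination would find but report nothing by phone. Or a subject may report a recurrence and then not attend. The second case is foreseeable: CIP 10.10.6 allows conditional disengagement, for example after relocation with telephone follow-up still acceptable, after which data collection requirements lapse.

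The rule on unconfirmed reports has a single category. It covers a report that an investigator examined and ruled out, which is evidence of no recurrence, and a report that nobody examined, which is not evidence either way. The separate listing, as worded, does not split the two.

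At stake is the reading of the only secondary endpoint that runs to 2 years. Missed cases can only lower the rate relative to its own definition, and that rate will be set beside 15% and 37%.

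**Working it through.** **1. The plan's own figure.** The inguinal benchmark is the 30-day benchmark plus a margin (Table 16): 8% + 7% = 15%. It reproduces. The ventral 37% has no formula; it is only placed between the upper confidence limit (23.1%) and the upper prediction limit (53.6%). The endpoint has no sample size or power statement.

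**2. How the handling of unexamined reports moves the rate.** Take n = 86 in one cohort, which is the SAP section 6 figure of 96 after 10% attrition. Carrying that to 2 years is an assumption. Assume 12 self-reports, of which 9 are examined and confirmed and 3 are never examined.

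| Handling of the 3 | Calculation | Rate |
|---|---|---|
| Non-events | 9/86 | 10.5% |
| Undetermined, out of the denominator | 9/(86 − 3) = 9/83 | 10.8% |
| Events | 12/86 | 14.0% |

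The text fixes the numerator at 9. It does not choose between the first two rows, because it does not say whether the three stay in the denominator.

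**3. How incomplete detection moves the rate.** Let s be the share of true recurrences that subjects report and e the share of reporters who are examined. Then

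recorded rate = true rate × S, with S = s × e.

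The documents give neither s nor e, so S is assumed from 0.5 to 0.9. The formula also takes every recurrence to arise after the in-person visits, which overstates the loss.

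| True rate | S = 0.9 | S = 0.7 | S = 0.5 |
|---|---|---|---|
| Ventral, literature mean 10.9% | 9.8% | 7.6% | 5.5% |
| Ventral, benchmark 37% | 33.3% | 25.9% | 18.5% |
| Inguinal, literature mean 0.6% | 0.5% | 0.4% | 0.3% |
| Inguinal, benchmark 15% | 13.5% | 10.5% | 7.5% |

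With S = 1 nothing is lost.

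**4. When the reading against the benchmark would change.** A recorded rate equal to the benchmark corresponds to a true rate of benchmark/S.
- Ventral: 37/0.9 = 41.1%; 37/0.7 = 52.9%. Both lie inside the plan's prediction interval (1.3% to 53.6%) but far above its literature mean.
- Inguinal: 15/0.9 = 16.7%; 15/0.7 = 21.4%. Both lie far above the upper prediction limit of 1.7%.

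So under-detection would alter the comparison only if ventral recurrence were much worse than the literature mean. The inguinal comparison would look favourable even with complete detection.

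**The case against.** The other side has a good case, and much of it stands.

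- **Reporters must be examined.** The in-person visit after a self-report is mandatory, so only those who miss it stay unexamined. This narrows the second route of loss. It does nothing for recurrences that are never reported, and no analysis rule covers the reporter who does not attend.
- **Unconfirmed reports are published.** A reader could add them back. But as worded the list mixes refuted with unexamined reports, so the right number to add back cannot be read from it.
- **Detection does not rest on two calls alone.** Recurrence is recorded on the AE form, device- or procedure-related AEs are reported after 30 days, and reoperation and readmission are followed to 2 years. These lower the loss by an amount the documents do not allow one to estimate.
- **The endpoint is descriptive.** There is no test and no success rule, so no formal conclusion of the trial depends on it. This stands.

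A reader might infer that the plan enters every unexamined subject as a non-event. The wording points that way: CIP 14.5 defines the rate as a proportion in all treated subjects, and the 30-day rule in SAP 7.4 treats a missed visit followed by later contact as no event. But no text says so for 2 years; the unconfirmed-report rule governs the numerator only.

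A reader might also infer that the rate is biased low against its benchmark. That would require the literature cohorts to have detected recurrence more completely than this trial will. The documents do not describe how those cohorts did it.

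**Conclusion.** The point holds in a limited form. The 2-year recurrence rate is at risk of being low against its own definition, because after 3 months an examination mainly depends on the subject's report. Two specification gaps add to this: refuted and never-examined reports share one category, and the 2-year denominator is not stated.

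The size is unknown. The spread of 10.5% to 14.0% and the detection shares above are illustrations with assumed inputs, not estimates for this trial. Comparability with 15% and 37% is not established in either direction.

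It would also go too far to say that the trial has no other long-term measure. Readmission, reoperation and device- or procedure-related AEs through 2 years are ancillary endpoints (CIP 5.3, SAP 4.3). Recurrence is the only long-term *secondary* endpoint.

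The change is still worth making: it is cheap, it alters a reported figure, and it can be specified before the 2-year analysis, which belongs to the later final report (CIP 14.2, SAP 7.2).

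**What to change.** In CIP 5.2.2 and SAP 7.9.3.1 and 7.9.3.5:

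1. Count a self-report as no recurrence only if an investigator examined the subject and refuted it. Classify a reported but unexamined case as undetermined.
2. State the denominator: confirmed recurrences over FAS subjects with 2-year contact and determined status, with a recurrence confirmed at any earlier time settling status. Say explicitly that phone-only subjects with nothing to report are included, under the label 'no self-reported recurrence'.
3. Add a sensitivity rate that counts unexamined reports as recurrences. Do not call it an upper bound, since unreported recurrences remain undetected.
4. Show both rates beside the benchmark, with the caveat that unreported cases are not captured and that ascertainment in the literature cohorts is not described.
5. If a rate is given for subjects examined in person at or after 1 year, label it a selected subset and do not compare it with the benchmark. That group is enriched with reporters, so its rate would tend to be too high.

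The cost is wording in two documents and one extra table, with no added visits. The reported rate may be slightly less favourable. The change does not recover recurrences that subjects never report; it makes that limit visible.
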